### 10.3.2. Reporting and Significant Figures

The concentration data as reported by the respective bioanalytical group should be used without rounding for all analysis. The non-compartmental parameters should not be reported to any greater accuracy than that of the concentration data. Default significant figures used for reporting in text and tables of the study report is 3 significant figures, except for time related parameters (h) and for geometric least squares mean ratios. Time related parameters (h) which will be presented with 2 decimal places. Geometric least squares ratios will be presented with 2 decimal places.

In the instance where the full parameters set (as defined in the analysis plan) cannot be estimated, the parameters that can be estimated will be reported. The term “NR” (not reported) may be used to denote that a value cannot be reported for a particular profile.

## 10.4. Pharmacokinetic/Pharmacodynamic (PK/PD) Analyses

The PK population will be used for all PK analyses. The ITT population will be used for all PD analyses. Using the PK population, scatter plots of the Week 16 actual values and change from Baseline in LDL cholesterol, particle size, and particle concentration, C4, FGF-19, and hs-CRP will be created versus total OCA plasma  $AUC_{0-6}$  and  $C_{max}$ . Additional PK/PD correlations may be identified and reported as deemed appropriate.

## 10.5. Bile Acid Pharmacodynamics

Analysis of conjugated and unconjugated bile acids may be undertaken per the protocol.

Bile acids include the following: total bile acids, UDCA (unconjugated-UDCA, glyco-UDCA, tauro-UDCA), chenodeoxycholic acid (CDCA) (unconjugated-CDCA, glyco-CDCA, tauro-CDCA), lithocholic acid (LCA) (unconjugated-LCA, glyco-LCA, tauro-LCA), cholic acid (CA) (unconjugated-CA, glyco-CA, tauro-CA), and deoxycholic acid (DCA) (unconjugated-DCA, glyco-DCA, tauro-DCA).

The bile acid assay comprises 15 sub-component bile acid concentrations that will be used to create totals of the individual bile acid concentrations. Bile acid concentrations will be converted from ng/mL units to micromolar units ( $\mu\text{M}$ ) as follows: Concentration ( $\mu\text{M}$ ) = Concentration (ng/mL) / molecular weight (MW). Bile acids totals should be summed on a molar basis (eg  $\mu\text{M}$ ). The MWs of the bile acids and their conjugates are presented in Table 1. For each bile acid, the assay will provide 3 subcomponent values that will need to be summed to produce the total bile acid value, as shown below in Table 1. As an example, the total UDCA concentration would be the sum of the glyco-, tauro-, and parent molecules.

**Table 1: Bile Acids and Their Sub-Components**

Derived	Sub-components (molecular weight)		
Total UDCA	Glyco-UDCA (449.6 g/mol)	Tauro-UDCA (499.7 g/mol)	UDCA (392.6 g/mol)
Total CDCA	Glyco-CDCA (449.6 g/mol)	Tauro-CDCA (499.7 g/mol)	CDCA (392.6 g/mol)
Total DCA	Glyco-DCA (449.6 g/mol)	Tauro-DCA (499.7 g/mol)	DCA (392.6 g/mol)
Total CA	Glyco-CA (465.6 g/mol)	Tauro-CA (515.7 g/mol)	CA (408.6 g/mol)
Total LCA	Glyco-LCA (433.6 g/mol)	Tauro-LCA (483.7 g/mol)	LCA (376.6 g/mol)

Individual total bile acids are derived as the sum of all bile acids (total UDCA, total CDCA, total DCA, total CA, and total LCA).

Total endogenous bile acids are derived as the sum of all bile acids, excluding all forms of OCA and UDCA.

Proportions of each bile acid are derived as the individual bile acid total divided by total bile acids (eg, total UDCA/total bile acids).

The ITT population will be used to summarize the total bile acid concentrations. The total bile acids, total endogenous bile acids, individual bile acid totals, and each of the bile acid proportions will be summarized by treatment group using descriptive statistics. BLQ values will be treated as one-half the lower limit of quantification [(LLOQ/2)]. For total UDCA and total endogenous bile acid, the change from Baseline concentrations within each treatment group will be compared using a paired t-test. Only samples from subjects that have a confirmed fasting (based on eCRF) of approximately 8 hours or more prior to the subject's visit will be included in the analysis.

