### 3.3.7. Pharmacodynamics

For 7 $\alpha$ -hydroxy-4-cholesten-3-one (C4) and fibroblast growth factor-19 (FGF-19), conjugated and unconjugated endogenous bile acids, and total bile acids:

- Observed values and change from Baseline at each DB post-Baseline visit

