### 7.5. OCA Pharmacokinetic (PK) Population

The PK Population will include all OCA treated subjects who consent to participate in the PK assessments and have at least one confirmed fasted OCA concentration. Subjects must have been fasting for at least 8 hours prior to dosing and must not have any major protocol deviations that potentially affect exposure levels.

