14.2.4.7.2	PK	Scatter Plot of Week 16 Change from Baseline in CRP versus Total OCA AUC 0-6
14.2.4.8.1.1	PK	Scatter Plot of Week 16 LDL Cholesterol Concentration versus Total OCA C max – SI Units
14.2.4.8.1.2	PK	Scatter Plot of Week 16 LDL Cholesterol Concentration versus Total OCA C max – CV Units
14.2.4.8.2.1	PK	Scatter Plot of Week 16 Change from Baseline in LDL Cholesterol Concentration versus Total OCA C max – SI Units
14.2.4.8.2.2	PK	Scatter Plot of Week 16 Change from Baseline in LDL Cholesterol Concentration versus Total OCA C max – CV Units
14.2.4.9.1	PK	Scatter Plot of Week 16 LDL Particle Size versus OCA C max
14.2.4.9.2	PK	Scatter Plot of Week 16 Change from Baseline in LDL Particle Size versus Total OCA C max
14.2.4.10.1	PK	Scatter Plot of Week 16 LDL Particle Concentration versus Total OCA C max
14.2.4.10.2	PK	Scatter Plot of Week 16 Change from Baseline in LDL Particle Concentration versus Total OCA C max
14.2.4.11.1	PK	Scatter Plot of Week 16 C4 versus Total OCA C max
14.2.4.11.2	PK	Scatter Plot of Week 16 Change from Baseline in C4 versus Total OCA C max
14.2.4.12.1	PK	Scatter Plot of Week 16 FGF-19 versus Total OCA C max
14.2.4.12.2	PK	Scatter Plot of Week 16 Change from Baseline in FGF-19 versus Total OCA C max
14.2.4.13.1	PK	Scatter Plot of Week 16 CRP versus Total OCA C max
14.2.4.13.2	PK	Scatter Plot of Week 16 Change from Baseline in CRP versus Total OCA C max

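### No OCA-versus-placebo difference or confidence interval is planned for C4, FGF-19 or bile acids; C4 and FGF-19 also have no planned by-arm summary, and the only bile acid test is within-arm

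*SAP*

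**What the plan says.** Section 2 lists evaluating the pharmacodynamics of OCA as an exploratory objective. Section 3.3.7 names C4, FGF-19, conjugated and unconjugated endogenous bile acids and total bile acids, and gives their endpoints as "Observed values and change from Baseline at each DB post-Baseline visit".

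Section 10.4 sets the population: "The ITT population will be used for all PD analyses". The analysis it then describes uses another one: "Using the PK population, scatter plots of the Week 16 actual values and change from Baseline in LDL cholesterol", continuing to C4, FGF-19 and hs-CRP, all plotted against total OCA exposure. Section 7.5 defines that population: "The PK Population will include all OCA treated subjects who consent to participate in the PK assessments". Section 10.1 adds that PK sampling is optional and at selected sites.

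Appendix A matches Section 10.4. C4 and FGF-19 appear in eight figures, all in the PK Population (for example "Scatter Plot of Week 16 C4 versus Total OCA C max" and "Scatter Plot of Week 16 FGF-19 versus Total OCA C max"), and in no table or named listing.

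For bile acids, Section 10.5 makes the analysis optional. If it is done, the totals and proportions are summarized descriptively by treatment group in ITT (Tables 14.2.18.1 to 14.2.18.3). One test is specified, for total UDCA and total endogenous bile acids only: "the change from Baseline concentrations within each treatment group will be compared using a paired t-test".

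**The concern.** Two things do not fit together. First, C4 and FGF-19 are endpoints at each post-Baseline visit with an ITT rule, but nothing carries that rule out. Their only specified outputs cannot include a placebo subject and cover Week 16 alone. Section 12 does not record this as a change from the protocol.

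Second, the one inferential method for bile acids tests change within an arm. Section 4 has all subjects start atorvastatin at the Week 4 visit. A later within-arm change is therefore the sum of any OCA effect, any atorvastatin effect and any drift over time. The randomized placebo arm receives the same atorvastatin, and it is what would separate these parts. The SAP plans no difference from it.

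At stake is the stated objective of evaluating OCA's pharmacodynamics. If the plan is followed as written, the report would show exposure plots in a self-selected OCA-only subset for two markers, and a set of within-arm p-values for two bile acid totals.

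**Working it through.** **Planned outputs by marker**

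| Marker (Section 3.3.7) | By-arm ITT summary | Test | OCA-minus-placebo estimate |
|---|---|---|---|
| C4 | none | none | none |
| FGF-19 | none | none | none |
| Total endogenous bile acids | yes | within-arm paired t | none |
| Total UDCA | yes | within-arm paired t | none |
| Total bile acids; total CDCA, CA, DCA, LCA | yes | none | none |

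So 2 of the 7 derived bile acid totals are tested, and none against placebo. The eight C4 and FGF-19 figures are 14.2.4.5.1–2, 14.2.4.6.1–2, 14.2.4.11.1–2 and 14.2.4.12.1–2.

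**Comparison with other endpoints.** Differences from placebo with CIs are planned for LDL measures (Section 9.1), liver biochemistry (9.3.1), inflammation and apoptosis markers (9.3.2), glycemic measures (9.3.3) and anthropometrics and blood pressure (9.3.6). hs-CRP is plotted beside C4 and FGF-19 in Section 10.4 and is compared with placebo in Section 9.3.2.

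**The plan's own figure.** The SAP gives no precision or power figure for any PD marker. Its only one is more than 97.3% power for LDLc (Section 5: increase 22, SD 24, n = 20, two-sided 0.05).
- As a within-arm t-test: noncentrality (22/24) × √20 = 4.10, df 19, power 97.29%. This reproduces the figure.
- As a two-sample comparison: noncentrality (22/24) × √10 = 2.90, df 38, power 80.6%.

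The point here does not depend on that figure. It shows only that Section 5, like Section 10.5, is framed within an arm.

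**What the paired t-test picks up.** The assumptions are mine: 20 analyzable subjects per arm, no OCA effect, and a change of s SDs (of the change score) shared by every arm. The paired t-test is a one-sample t-test on changes with df 19 and noncentrality s√20. An OCA-versus-placebo t-test has noncentrality 0 whatever s is. The last column is r(1 − r), where r is the within-arm rejection rate: the chance that a given OCA arm is significant while placebo is not.

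| Shared change s | Within-arm test rejects (r) | OCA-versus-placebo test rejects | OCA arm rejects, placebo does not |
|---|---|---|---|
| 0 | 5.0% | 5% | 0.050 × 0.950 = 4.8% |
| 0.25 | 18.6% | 5% | 0.186 × 0.814 = 15.1% |
| 0.5 | 56.5% | 5% | 0.565 × 0.435 = 24.6% |
| 0.75 | 88.9% | 5% | 0.889 × 0.111 = 9.9% |
| 1.0 | 98.9% | 5% | 0.989 × 0.011 = 1.1% |

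**Precision of the missing estimate.** The 95% CI half-width of an unadjusted arm difference is t(0.975, 2n − 2) × √(2/n) in SD units. It is 0.64 SD with 20 per arm and 0.75 SD with 15 per arm.

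**The case against.** A reader might infer that placebo PD data are never used, or that the outputs give no randomized information on any PD marker. The SAP does not support that:

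- Section 10.5 and Tables 14.2.18.1 to 14.2.18.3 show every bile acid total and proportion by randomized arm in ITT. An unadjusted difference can be read from them. What is missing is a planned contrast and its CI.
- LDL measures and hs-CRP, which are also plotted in Section 10.4, are compared with placebo in Sections 9.1 and 9.3.2. The gap is confined to the Section 3.3.7 list.

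Other points against the concern also carry weight:

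- Section 6.2.8 makes all p-values and CIs descriptive, and Section 10.5 nowhere says that a significant paired test will be read as an OCA effect.
- Cardiovascular risk scores and markers (Sections 9.3.7 and 9.3.8) are likewise summarized without a test, and Section 3.3.7 promises no between-arm contrast.
- Section 6.1 promises by-subject listings of individual and external laboratory data in general. The missing C4/FGF-19 listing may be only an incomplete Appendix A.
- No PD sampling schedule is in the SAP. How many visits before Week 16 go unreported therefore cannot be counted with confidence.

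It can also be said that running the same test in placebo would expose a shared change. That holds only in part. Under the assumptions above, a shared 0.5 SD change still leaves a 24.6% chance, for each OCA arm, of significance there and not in placebo. Setting p-values side by side is no substitute for the difference.

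**Conclusion.** The point stands in this form. No OCA-versus-placebo difference or CI is planned for any Section 3.3.7 marker. C4 and FGF-19 have no by-arm summary, although they are endpoints with an ITT rule. The only bile acid test mixes any OCA effect with time and, after Week 4, with atorvastatin.

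The C4 and FGF-19 gap is an inconsistency between Sections 3.3.7, 10.4 and Appendix A and rests on no assumption. The bile acid part concerns the choice of method. Its size (56.5% against 5% at a shared change of 0.5 SD) is illustrative, because the SAP gives no variance or expected change for these markers.

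The change is worth making before database lock. Its importance is moderate: the endpoints are exploratory, inference is descriptive, and the trial's primary result is unaffected.

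**What to change.** In Sections 10.4 and 10.5 and in Appendix A:

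1. Add ITT summaries of C4 and FGF-19 by treatment group at each visit where they are measured, and a by-subject listing.
2. For C4, FGF-19, total endogenous bile acids and the five individual bile acid totals, present the OCA-minus-placebo difference with 95% CI for each dose. Use the Section 6.2.3 ANCOVA (log scale if skewed) or the Wilcoxon/Hodges-Lehmann method of Section 9.3.2.
3. Show Week 16 and, if samples were taken then, Week 4 before atorvastatin starts.
4. Keep the paired t-test, labelled as a description of within-arm change only.
5. Keep the exposure scatter plots as they are.

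The cost is SAP wording and a few more tables from endpoints the SAP already defines. The downside is more unadjusted contrasts, up to 8 markers × 3 doses × 2 visits = 48. They should be labelled exploratory and descriptive under Section 6.2.8. With about 20 per arm the intervals will be wide.

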## 11. SAFETY ANALYSES

All safety analyses will be based on the Safety Population. The AE, vital signs, clinical laboratory evaluations, and ECG analyses are defined as secondary endpoints per the protocol. The anthropometric measures, blood pressure, and cardiovascular risk scores are defined as exploratory efficacy endpoints per the protocol.

## 11.1. Extent of Exposure

### 11.1.1. Investigational Product (OCA or Placebo)

Subjects may change their OCA or placebo dosing regimen while on treatment during the DB if deemed necessary by the Investigator. The duration of investigational product exposure at DB will be calculated as follows:

- Exposure to investigational product = {[ (Date of last investigational product dose – Date of 1st investigational product dose) +1 ]}

Total investigational product (mg) exposed to subject will be calculated by adding the doses taken by a subject during the study and will be summarized using descriptive statistics.

Subject's overall compliance (%) with investigational product will be calculated as follows:

- (# of investigational product tablets consumed during study / # of investigational product tablets expected to be consumed during study) × 100

where # of investigational product tablets consumed during study = # of days on treatment based – any missed doses, and # of investigational product tables expected to be consumed during study is the total # of days on study drug based on treatment start and stop dates, excluding drug holidays

Subject compliance with investigational product will be summarized by treatment group using descriptive statistics. Percent compliance will be summarized separately for subjects who completed the study versus those who withdrew early so as to distinguish between those subjects who were compliant throughout the entirety of the study versus those who were compliant until they withdrew from the study.

Additional summaries will present the number and percentage of subjects with any drug interruption and drug discontinuation. Denominators for calculating percentages will be based on the number of subjects who received at least one dose in the treatment group summarized.

All exposure data will be presented in a by-subject data listing.

### 11.1.2. Atorvastatin

The weighted average daily dose (WADD) of atorvastatin, the study medication, will be calculated as:

$$\text{WADD} = \frac{\sum_{\text{all doses}} (\text{dose} \times \text{number of days at specified dose})}{(\text{total number of days on atorvastatin (including any days on drug holiday)})}$$

For example, for a subject on 10 mg atorvastatin for 6 weeks and 20 mg atorvastatin for 6 weeks without any days off atorvastatin, WADD would be calculated as:

$$\text{WADD} = [(10 \text{ mg} \times 42 \text{ days}) + (20 \text{ mg} \times 42 \text{ days})] / (84 \text{ days}) = 15 \text{ mg}$$

The WADD will also be categorized as  $\leq 12$  mg atorvastatin,  $> 12$  mg to  $20$  mg atorvastatin,  $> 20$  mg atorvastatin.

Subject's overall compliance (%) with study medication will be calculated as follows:

- (# of study medication tablets consumed during study / # of study medication tablets expected to be consumed during study) × 100

Subject compliance with atorvastatin will be summarized by treatment group using descriptive statistics. Percent compliance will be summarized separately for subjects who completed the study versus those who withdrew early so as to distinguish between those subjects who were compliant throughout the entirety of the study versus those who were compliant until they withdrew from the study.

Additional summaries will present the number and percentage of subjects with any drug interruption and drug discontinuation. Denominators for calculating percentages will be based on the number of subjects who received at least one dose in the treatment group summarized.

All exposure data will be presented in a by-subject data listing.

## 11.2. Adverse Events (AEs)

AE data will be collected from the time that signed informed consent is obtained until the subject fully completes her/his study participation of the study.

Pre-treatment AEs and treatment-emergent adverse events (TEAEs) will be summarized. TEAEs are defined as any AEs that newly appear, increase in frequency, or worsen in severity following initiation of investigational product. If it cannot be determined whether the AE is Treatment-Emergent due to a partial onset date, then it will be counted as treatment-emergent. Verbatim terms on eCRFs will be mapped to preferred terms and system organ classes using MedDRA (version 18.1).

Summaries that are displayed by system organ class and preferred terms will be ordered by descending order of incidence, for all OCA-treated patients, of system organ class and by preferred terms within each system organ class. Summaries of the following types will be presented by treatment group:

- Overall summary of TEAEs
- Subject incidence of pre-treatment AEs and the total number of entries by MedDRA system organ class and preferred term
- Subject incidence of TEAEs and the total number of entries by MedDRA system organ class and preferred term
- Subject incidence of drug-related TEAEs by MedDRA system organ class and preferred term. Related AEs are those with relationships reported as “Definite,” “Probable,” “Possible,” or with a missing relationship. This analysis will be performed for relationship to investigational product and to atorvastatin.
- Subject incidence of liver biopsy-related TEAEs by MedDRA system organ class and preferred term. Related AEs are those with relationships reported as “Definite” or AEs with a missing relationship.
- Subject incidence of serious TEAEs by MedDRA system organ class and preferred term

- Subject incidence of TEAEs leading to investigational product withdrawal by MedDRA system organ class and preferred term
- Subject incidence of TEAEs leading to study medication withdrawal by MedDRA system organ class and preferred term
- Subject incidence of TEAEs leading to study discontinuation by MedDRA system organ class and preferred term
- Subject incidence of TEAEs leading the investigational product withdrawal, study medication withdrawal, or study discontinuation by MedDRA system organ class and preferred term
- Subject incidence of TEAEs by MedDRA system organ class, preferred term, and maximum severity will be presented. At each level of subject summarization, a subject is classified according to the maximum severity if the subject reported one or more events. AEs with missing severity will be considered severe for this summary.

The summaries above will be repeated presenting only preferred term ordered by descending order of incidence, for all OCA treated subjects, excluding system organ class.

In addition, other than Follow-up TEAEs, these summaries will be repeated for the time period up to Week 4, to evaluate the effects of OCA alone and in combination with atorvastatin. These analyses will include TEAEs with date of onset prior to the start of atorvastatin.

The following listings will be presented by subject:

- All AEs
- Serious AEs (subset of the AEs where serious is marked as “Yes”)
- Death information will be provided in a separate listing, should any deaths occur
- AE’s leading to withdrawal of investigational product
- AEs leading to withdrawal of study medication
- AEs leading to Study Discontinuation

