## **4. STUDY DESIGN AND PLAN**

This is a Phase 2, double-blind, randomized, placebo-controlled, multicenter study, evaluating the effects of OCA, and the subsequent addition of statin therapy, on lipoprotein metabolism in subjects with NASH with fibrosis stage 1 to 4, but no evidence of hepatic decompensation, in the DB phase, followed by an open-label LTSE phase to evaluate long term safety and efficacy.

Approximately 80 subjects with histological evidence of definite or probable NASH, who meet all inclusion and none of the exclusion criteria will be enrolled in the study. The histological evidence of definite or probable NASH will be based on the central read of a liver biopsy obtained no more than 1 year prior to randomization and a nonalcoholic fatty liver disease activity score (NAS) of 4 or greater. Subjects not using statin therapy (ie, statin-free) and statin-treated subjects may be enrolled. Statin-treated subjects will be required to stop statin treatment (after signing informed consent) for up to 5 weeks, including a 4-week statin washout period, prior to Randomization/Day 1.

Subjects will have a screening period of up to 5 weeks prior to Randomization/Day 1. At the Randomization (Day 1) Visit, subjects will be randomized in a 1:1:1:1 ratio to receive OCA 5 mg, OCA 10 mg, OCA 25 mg, or placebo, orally, once daily, for 16 weeks. Randomization will be stratified by the pre-randomization fasting serum LDLc ( $\leq$ 125 mg/dL or  $>$ 125 mg/dL) and baseline fibrosis stage (stage 1, 2 or stage 3, 4).

[figure not shown]
Subjects will attend on-site clinic visits at Weeks 2, 4, 8, 12, and 16 and will be contacted at Weeks 6, 10 and 14 to assess safety and treatment compliance. At the Week 4 Visit, all subjects will initiate treatment with atorvastatin at a dose of 10 mg once daily. At the Week 8 Visit, atorvastatin will be increased to 20 mg once daily (if 10 mg daily is tolerated), and continued for an additional 4 weeks. After 4 weeks of treatment at 20 mg, the atorvastatin dose may be titrated (up or down) as clinically indicated. The final visit during the DB phase will occur at Week 16, after which subjects may continue into the open-label LTSE.

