### 7.3. Safety Population

The Safety Population will include all subjects who receive any amount of investigational product within the DB phase. Treatment assignment will be based on the actual treatment received.

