14.2.18.2	ITT	Summary of Bile Acids and Bile Acid Sub-components
14.2.18.3	ITT	Summary of Bile Acid Proportions
14.3		Safety Data
14.3.1	Safety	Summary of Investigational Product Exposure
14.3.2	Safety	Summary of Atorvastatin Exposure
14.3.3.1	Safety	Summary of Prior and New Concomitant Medications
14.3.3.2	Safety	Summary of New Concomitant Medications
14.3.1		Displays of Adverse Events
14.3.1.1.1	Safety	Overall Summary of Treatment-Emergent Adverse Events
14.3.1.1.2	Safety	Overall Summary of Treatment-Emergent Adverse Events Up to Week 4
14.3.1.2.1	Safety	Summary of Treatment-Emergent Adverse Events by System Organ Class and Preferred Term
14.3.1.2.2	Safety	Summary of Treatment-Emergent Adverse Events by Preferred Term
14.3.1.2.3	Safety	Summary of Treatment-Emergent Adverse Events Up to Week 4 by System Organ Class and Preferred Term
14.3.1.2.4	Safety	Summary of Treatment-Emergent Adverse Events Up to Week 4 by Preferred Term
14.3.1.3.1	Safety	Summary of Investigational product-related Treatment-Emergent Adverse Events by System Organ Class and Preferred Term
14.3.1.3.2	Safety	Summary of Investigational product-related Treatment-Emergent Adverse Events by Preferred Term
14.3.1.3.3	Safety	Summary of Investigational product-related Treatment-Emergent Adverse Events Up to Week 4 by System Organ Class and Preferred Term
14.3.1.3.4	Safety	Summary of Investigational product-related Treatment-Emergent Adverse Events Up to Week 4 by Preferred Term
14.3.1.4.1	Safety	Summary of Study Medication-related Treatment-Emergent Adverse Events by System Organ Class and Preferred Term
14.3.1.4.2	Safety	Summary of Study Medication-related Treatment-Emergent Adverse Events by Preferred Term
14.3.1.5.1	Safety	Summary of Liver biopsy-related Treatment-Emergent Adverse Events by System Organ Class and Preferred Term
14.3.1.5.2	Safety	Summary of Liver biopsy-related Treatment-Emergent Adverse Events by Preferred Term
14.3.1.6.1	Safety	Summary of Treatment-Emergent Serious Adverse Events by System Organ Class and Preferred Term
14.3.1.6.2	Safety	Summary of Treatment-Emergent Serious Adverse Events by Preferred Term
14.3.1.6.3	Safety	Summary of Treatment-Emergent Serious Adverse Events Up to Week 4 by System Organ Class and Preferred Term

Table Number	Population	Table Title
14.3.1.6.4	Safety	Summary of Treatment-Emergent Serious Adverse Events Up to Week 4 by Preferred Term

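### A blank atorvastatin causality entry counts as related even for events before the first atorvastatin dose

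*SAP*

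**What the plan says.** Four statements in the SAP combine here.

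- **Treatment-emergent window (Section 11.2):** "TEAEs are defined as any AEs that newly appear, increase in frequency, or worsen in severity following initiation of investigational product". Investigational product is OCA or placebo, taken from Day 1: "OCA 5 mg, OCA 10 mg, OCA 25 mg, or placebo, orally, once daily, for 16 weeks" (Section 4).
- **Relatedness rule (Section 11.2):** Definite, Probable, Possible, "or with a missing relationship. This analysis will be performed for relationship to investigational product and to atorvastatin".
- **Start of atorvastatin (Section 4):** "At the Week 4 Visit, all subjects will initiate treatment with atorvastatin at a dose of 10 mg once daily".
- **Output (Appendix A, Table 14.3.1.4.1):** "Summary of Study Medication-related Treatment-Emergent Adverse Events by System Organ Class and Preferred Term", with a preferred-term version as Table 14.3.1.4.2. Section 11.1.2 shows that study medication means atorvastatin: "The weighted average daily dose (WADD) of atorvastatin, the study medication, will be calculated as". Both tables use the Safety Population, which does not require atorvastatin intake: "The Safety Population will include all subjects who receive any amount of investigational product within the DB phase" (Section 7.3).

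Section 11.2 also repeats its summaries for the period up to Week 4: "These analyses will include TEAEs with date of onset prior to the start of atorvastatin".

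**The concern.** Counting missing causality as related is a cautious convention, and it makes sense when the subject was exposed to the drug in question. For study atorvastatin, no subject is exposed in the first four weeks. A blank entry in that period says nothing about atorvastatin, yet the rule turns it into an atorvastatin-related event.

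The stake is the reading of one pair of descriptive safety tables. Section 2 sets as a secondary objective the safety and tolerability of OCA, both alone and combined with atorvastatin, and Section 11.2 uses the start of atorvastatin to separate the two periods. Events from the OCA-alone period that appear under atorvastatin blur that separation. If early events with blank entries were more frequent in one arm, apparent statin-related incidence would be higher in that arm for no pharmacological reason.

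**Working it through.** The SAP states no figure on this point, so there is none to reproduce. The check is first one of logic, then an illustration of scale.

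**Does any clause prevent it?**

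1. Take a TEAE in Week 2 with the atorvastatin relationship blank. It follows the first investigational product dose, so it is treatment-emergent (Section 11.2).
2. The relationship is missing, so it is related. The rule names atorvastatin explicitly (Section 11.2).
3. The subject took investigational product, so is in the Safety Population (Section 7.3).
4. The titles of Tables 14.3.1.4.1 and 14.3.1.4.2 carry no onset condition (Appendix A).
5. The only onset condition tied to atorvastatin belongs to the additional up-to-Week-4 summaries. It selects early events for those extra tables and removes none from the full-period ones.

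The event is therefore counted as atorvastatin-related. The same chain holds for a subject who leaves before Week 4 and never receives atorvastatin.

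**Do the up-to-Week-4 repeats add a second problem?** Read literally, the text of Section 11.2 repeats the atorvastatin-related summary for the pre-atorvastatin period. Appendix A lists up-to-Week-4 versions for investigational product-related events (14.3.1.3.3 and 14.3.1.3.4) but none for study medication-related events (14.3.1.4.x) or for study medication withdrawal (14.3.1.10.x). The text and the table list differ, but the table list already omits the meaningless output.

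**Scale.** Inputs from the SAP: 16 weeks of double-blind treatment and atorvastatin from Week 4 (Section 4); 20 subjects per group (Section 5).

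- Share of the double-blind phase before atorvastatin: 4/16 = 25%.
- Weight of one subject in an arm of 20: 1/20 = 5 percentage points.

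Two further inputs are assumptions, because the SAP gives neither: *p*, the proportion of subjects with a TEAE before Week 4 (20% to 60%), and *m*, the probability that the atorvastatin causality of that event is blank. With one such event per affected subject, the expected number wrongly counted per arm is 20 × *p* × *m*:

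| *m* (blank) | *p* = 20% | *p* = 40% | *p* = 60% |
|---|---|---|---|
| 0% | 0 | 0 | 0 |
| 5% | 0.2 | 0.4 | 0.6 |
| 20% | 0.8 | 1.6 | 2.4 |
| 100% | 4 | 8 | 12 |

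The range runs from nil to large and is driven almost entirely by *m*.

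**The case against.** The strongest reply is that the harm depends on something the SAP does not show. The eCRF field, its options and the query rules are not described. If investigators record a causality for every event, the missing-data rule never operates and the tables are correct. That stands, and it means the effect may be nil.

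It is also true that the tables are descriptive (Section 6.2.8), that the overall TEAE tables do not use atorvastatin causality, and that the planned AE listings (16.2.7.1 and 16.2.7.5) offer a route for tracing a misattributed event. These points limit the consequence but do not make the rule right.

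A reader might infer more than the document supports:

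- *That a quarter of TEAEs, or some minimum number of subjects, will be misattributed.* The 25% is the share of time before atorvastatin, not a misattribution rate. Without a blank rate the lower bound is zero.
- *That a secondary objective on atorvastatin's own tolerability is compromised.* The objective in Section 2 concerns OCA, alone and with atorvastatin. It is served mainly by analyses that do not use atorvastatin causality.
- *That every atorvastatin-related event should be filtered by onset.* A TEAE can be an event that worsens. One that began before Week 4, worsened on atorvastatin and was rated Possible could be lost if recorded under its first onset date. That would override an explicit judgement.
- *That the Safety Population is the wrong denominator.* Restricting it to atorvastatin takers conditions on remaining in the study to Week 4, which follows randomization and may differ by dose. It is a trade-off, not a correction.

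**Conclusion.** The point holds in a narrow form. The rule as stated labels a blank-causality event before any study atorvastatin, or in a subject who never took it, as atorvastatin-related, and no other clause prevents this. The fault lies only in applying the missing-as-related convention to atorvastatin without a timing condition; the convention itself is sound.

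The size cannot be fixed from the document. It is zero if causality is always recorded, and otherwise about 5 percentage points per affected subject, assuming arms of 20 as planned. The primary endpoint is untouched. The mismatch over the up-to-Week-4 repeats is loose wording, since Appendix A does not plan the table concerned.

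**What to change.** Add to Section 11.2: *For the atorvastatin-related summary, a missing relationship is counted as related only if the onset or worsening of the event is on or after the subject's first atorvastatin dose. If a partial date leaves the timing relative to that dose undetermined, the event is counted as after it, provided the subject took atorvastatin.*

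Leave three things unchanged: Definite, Probable and Possible as the investigator reported them; missing-as-related for investigational product; and the Safety Population denominator.

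In the same section, state that the up-to-Week-4 repeats do not include the study medication-related summary, in line with Appendix A.

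The cost is small: one rule, one clause and a date comparison. The up-to-Week-4 tables already require the start date of atorvastatin. The partial-date provision may retain a few early events whose timing is unclear, which keeps the rule cautious. Blank-causality events known to precede atorvastatin, with no later worsening, would fall to zero in these tables.
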